8.3.24. Clinical Validation Inventory for Study Admission

The PI or designee will complete the Diagnostic Validation Workbook as part of the Clinical Validation Inventory for Study Admission (C-VISA™) at Visit 1. This workbook is a structured method for assessing and documenting study eligibility based on the criteria given in [Section 7](#).

8.4. Study Requirements and Restrictions

8.4.1. Prohibited Medications

Use or expected use of any of the following medications (including generic equivalents or alternative brand names) within 60 days prior to screening or during the study period is prohibited.

- All prescription or over-the-counter (OTC) agents taken for the purpose of weight reduction, including (but not limited to) the following anti-obesity agents:
 - Prescription drugs such as orlistat (Xenical), sibutramine (Meridia), Belviq (lorcaserin); and phentermine (Adipex-P, Ionamin, Pro-Fast SA, Pro-Fast SR, Fastin, Oby-Trim, Zantryl, Teramine, Phentride, Phentercot, Obephen, Oby-cap), Qsymia (phentermine and topiramate)
 - Over-the-counter anti-obesity agents (eg, herbal supplements or other alternative remedies such as Cortislim, Dexatrim, Acutrim, Orlistat)
- Systemic steroids administered by oral, intravenous, or intramuscular route
- Antipsychotic agents including clozapine, mesoridazine, chlorpromazine, or thioridazine
- Zyprexa oral disintegrating tablets, Zyprexa Relprevv™ intramuscular injection (long-acting), or Zyprexa IntraMuscular injection (short-acting)
- Topiramate (Topamax®); Calcitonin (eg, Miacalcin®), Exenatide (Byetta®); Sulfonylureas (eg, Diamicon®, Amaryl®, Glucotrol®, Micronase®); Meglitinides (eg, Starlix®, Prandin®); Metformin or any hypoglycemic agent

Use of opioid agonists (eg, codeine, oxycodone, tramadol, or morphine) within 14 days before screening is prohibited. Use of opioid antagonists, including naltrexone (any formulations) and

naloxone within 60 days before screening through the follow-up visit is prohibited. Note: during the study period, opioid agonists should be avoided (refer to [Section 8.4.4](#)).

Use of hypnotic agents for insomnia (eg, benzodiazepines, zolpidem, trazodone) is permissible. Short half-life benzodiazepines are preferable for the treatment of insomnia over long half-life benzodiazepines due to the potential for lingering effects on daytime functioning and study assessments.

Treatment of agitation and/or anxiety with benzodiazepines is permissible, but the dose should be kept as stable as possible throughout the study so as not to interfere with daytime functioning and study assessments. Special care should be taken with dosing of benzodiazepines on study visit days so as not to influence efficacy ratings (eg, PANSS); doses of benzodiazepines should be withheld if scheduled to be taken within several hours of a PANSS rating.

Use of moderate to strong inducers or inhibitors of cytochrome P450 (CYP) 3A4 (prescription medications, OTC medications, or dietary supplements) within 30 days before randomization through follow-up is prohibited. A partial list of CYP3A4 modulators is provided in [Appendix G](#).

Medications that are contraindicated with olanzapine use or exhibit drug-interaction potential with olanzapine will be defined and prohibited at the discretion of the PI.

See [Section 8.3.5](#) for details regarding the concomitant medication review.

8.4.2. Contraception

All subjects must agree to use an acceptable method of contraception for the duration of the study. Subjects who are abstinent must agree to use an acceptable contraceptive method should they become sexually active. The following are considered acceptable methods:

- Condom (barrier method) plus
 - Intrauterine device (IUD)or
 - Hormonal contraceptive (such as birth control pills or patches, a vaginal ring, or a contraceptive implant)

Sexually active male subjects must agree use a condom in addition to his partner's normal use of contraception.

Exemptions: Subjects who are surgically sterile are exempt from the requirement to use contraception. Women who have undergone a hysterectomy, bilateral tubal ligation, or bilateral salpingo-oophorectomy are considered surgically sterile. Men who have undergone a vasectomy are considered surgically sterile. In addition, women who are postmenopausal are also exempt from the requirement to use contraception.

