7. SELECTION AND WITHDRAWAL OF SUBJECTS

7.1. Subject Inclusion Criteria

Each subject must meet all of the following inclusion criteria to be qualified to participate in this study.

1. Subject is willing and able to provide informed consent; subject has signed the main informed consent form (ICF) before initiation of any study specific procedures (see [Section 17.3](#))
2. Subject is age 18 to 50 years, inclusive, at screening
3. Subject has a body mass index (BMI) of 17.0-30.0 kg/m², inclusive, at screening
4. Subject has a diagnosis of schizophrenia (based on Diagnostic and Statistical Manual of Mental Disorders [DSM] criteria) that is clinically stable as evidenced by both of the following:
 - No hospitalizations for acute exacerbations of schizophrenia within 2 months before screening
 - Clinical Global Impressions-Severity (CGI-S) score of ≤ 3 (mild) at screening and Visit 2
5. Subject has a total Positive and Negative Syndrome Scale (PANSS) score ≤ 80 at screening and Visit 2
6. Subject has stable positive symptoms as shown by a score ≤ 4 on PANSS for items related to delusion, hallucination, conceptual disorganization, and unusual thought content, at screening and Visit 2.
7. Subject currently resides in a stable residence or living arrangement, has been in this residence/living arrangement for at least 8 weeks prior to screening, and the residence/living arrangement is not anticipated to change during the study.
8. Subject agrees to maintain current level of fitness or exercise regimen for the duration of the study
9. Subject reports a stable body weight for at least 3 months prior to screening (change $\leq 5\%$) and from screening to Visit 2 (change ≤ 1 kg)
10. Subject agrees to use an acceptable method of contraception for the duration of the study (as described in [Section 8.4.2](#)).
11. Subject must have an informant or caregiver who meets the following criteria:
 - a. Informant or caregiver will be in contact with the subject several times per week.
 - b. If necessary, the informant or caregiver will accompany the subject to visits.
 - c. Informant or caregiver will help ensure maximum subject adherence to study procedures.

12. Subject is fluent in the language (oral and written) in which assessments will be made, and can be reliably rated.

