- Personal or family history of neuroleptic malignant syndrome
 - Dyslipidemia, defined for this study as total cholesterol >280 mg/dL or triglycerides >500 mg/dL, at screening
 - Inflammatory bowel disease or any other gastrointestinal (GI) disorder associated with weight loss, anorexia nervosa, bulimia nervosa, or binge eating disorder
 - Neurologic conditions including the following:
 - History of seizure disorder or a condition associated with seizures
 - History of brain tumor, subdural hematoma or other clinically significant neurological condition within the 12 months prior to screening
 - Head trauma with loss of consciousness within the 12 months prior to screening
 - Active acute or chronic central nervous system (CNS) infection
 - Stroke within the 6 months prior to screening
8. Subject has a cardiac condition that might confound the results of the study or pose additional risk when administering the investigational agents to the subject or preclude successful completion of the study. Such conditions include the following:
- Clinically significant cardiac arrhythmia, cardiomyopathy, or cardiac conduction defect; a history of myocardial infarction or unstable angina; or clinically significant ECG abnormality at Visit 1 or Visit 2.
 - QT interval >450 msec for men and >470 msec for women, as corrected by the Fridericia formula (QTcF), observed at Visit 1 or Visit 2.
9. Subject has a laboratory abnormality that would compromise the well-being of the subject, or has any of the following specific laboratory results at Visit 1 or Visit 2:
- Aspartate aminotransferase (AST) or alanine aminotransferase (ALT) value ≥ 3 times the upper limit of the laboratory normal reference range
 - Absolute neutrophil count (ANC) $\leq 1.5 \times 10^3$ per μL at Visit 1 and $< 1.0 \times 10^3$ per μL at Visit 2
 - Platelet count $\leq 75 \times 10^3$ μL
 - Serum creatinine >2.5 mg/dL
 - Positive pregnancy test result
10. Subject is pregnant or breastfeeding or is planning to become pregnant within 60 days of the last study drug administration
11. Subject has had any GI surgical procedures within one year prior to screening
12. Subject has had a surgical procedure for weight loss or is planning to have liposuction during the study

13. Subject has had significant changes in diet or exercise regimen within the 6 weeks prior to screening or plans to join a weight management program during the study.

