7.3. Subject Withdrawal

A subject may be discontinued from the study at any time if the subject, PI (or designee), or sponsor determines that it is not in the best interest of the subject to continue participation. If a subject has an $ANC < 1.0 \times 10^3$ per μL at anytime from Visit 2 to Visit 25, the PI (or designee) should discontinue the subject from participation immediately.

If a subject withdraws from the study for any reason, any ongoing AEs and/or a low ANC will be followed until resolution, until deemed stable by the PI, or until the subject is deemed by the PI to be lost to follow-up. If, in the opinion of the PI, it is necessary to monitor a subject beyond the

safety follow-up visit, the follow-up period may be extended as necessary. In such instances, the sponsor and the PI will agree to an acceptable follow-up schedule.

In the event that a subject chooses to withdraw from the study, the PI (or designee) should make a reasonable effort to ascertain the reason(s) for withdrawal while fully respecting the subject's rights. The subject should complete an ET visit when possible and subjects should be encouraged to return for follow-up visits 2 and 4 weeks after the ET visit. If the subject fails or refuses to return to the study center, an attempt must be made to contact the subject by telephone in order to assess as many safety and efficacy parameters as possible. All data collected over the telephone must be documented and kept in the subject's record.

The PI must maintain a record of all subjects who fail to complete the study. A full explanation of the reason for study discontinuation will be made on the appropriate electronic case report form (eCRF). If a subject is lost to follow-up, a reasonable attempt to contact the subject must be made and documented.

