8.1.2. Part B (Active ALKS 3831 Treatment and Safety Follow-up Periods)

After completion of Part A (ie, at Visit 13), subjects will transition into Part B and will continue onto a 12-week active treatment period during which all subjects will receive ALKS 3831 (ie, olanzapine + samidorphan). Subjects who had been receiving ALKS 3831 during the double-blind period will continue on the same dose for the 12-week active treatment period. Subjects who had been receiving olanzapine + placebo in the double-blind period will continue on the same dose of olanzapine and will be transitioned from placebo to samidorphan (at the highest dose).

At Visit 13 (Study Day 92), subjects will be admitted for a 2-night inpatient stay to allow for monitoring following initiation of samidorphan dose in subjects originally assigned to the olanzapine + placebo group. Because treatment assignments in the double-blind period must remain blind until all subjects have completed Part A or been discontinued from the study, the inpatient stay is required for all subjects. After discharge (Study Day 94), subjects will return 5 days later for Visit 16 (Study Day 99). After Visit 16, subjects will be seen weekly for the next 3 weeks (Visits 17-19) and then at 2-week intervals for the remainder of the study (Visits 20-25).

The subject will take the final samidorphan dose the night before Visit 23 (Study Day 176). No samidorphan dose will be administered onsite during Visit 23. Olanzapine dosing will continue uninterrupted. Two safety follow-up visits will occur 2 and 4 weeks after Visit 23. Any subject who prematurely discontinues from the study during Part B will be asked to return to the clinic for an ET visit and follow-up visits 2 and 4 weeks after the ET visit.

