9. TREATMENT OF SUBJECTS

9.1. Study Drug Dose and Administration

Study drugs include samidorphan and matching placebo tablets, and olanzapine tablets, all for oral administration. Samidorphan is a Schedule II substance, and should be stored, dispensed, and otherwise handled in accordance with the associated regulations.

Olanzapine will be prescribed by the PI and will be dispensed for oral administration by study staff.

During the inpatient stays, study drug will be dispensed once daily, and the time of administration will be at the discretion of the clinic staff. Time of administration at any visit (inpatient or outpatient) may be adjusted as needed to accommodate post-dose measurements. Before being discharged from each inpatient stay, and at each outpatient post-randomization study visit until Visit 23/ET, all subjects will receive blister cards containing samidorphan or placebo for self administration. Subjects will be instructed to take 2 tablets per day from the blister card and their olanzapine tablet(s) once daily in the evening or at bedtime until Visit 23. The subject will take the final samidorphan dose the night before Visit 23. No samidorphan dose will be administered onsite during Visit 23/ET. Olanzapine dosing will continue uninterrupted. Two safety follow-up visits will occur 2 and 4 weeks after Visit 23. Any subject who prematurely discontinues from the study during Part B will be asked to return to the clinic for an ET visit and follow-up visits 2 and 4 weeks after the ET visit.

Subjects should take all study drug tablets (olanzapine and samidorphan/placebo) orally and at the same time. Subjects should be advised that somnolence may occur with dosing and thus they should avoid driving or operating heavy machinery until they have determined how the study drug affects them.

Subjects will be instructed to keep all unused tablets in their blister card and not to mix tablets between blister cards and bottles. Subjects will also be instructed to return unused tablets to the site when they return for their next visit. If dosing occurs at this visit, the dose should be taken from subjects' next blister card. The dose should not be taken from the blister card the subjects are returning.

If a dose is missed or forgotten, subjects will be instructed to resume the regular dosing schedule the following evening. Subjects will be instructed not to take a double dose to try to "make up" for a missed dose.

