3.11.1.3 Early termination (ET) visit

An early termination (ET) visit can be mapped to a scheduled visit and be used for analysis and summaries only if there is no valid value already at the mapped visit.

A mapped ET visit will be treated as a scheduled visit to be included in table summaries. Otherwise, it will be treated as an unscheduled visit.

Two rules will be used to map an ET visit.

First, a 7-day (inclusive) window (\leq last dose date + 7) will be used to determine if the assessment at the ET visit is considered to be an on-treatment result. If an ET visit is within 7 days after the last dose of samidorphan/placebo, it will be considered as a valid on-treatment

visit.

Second, visit windows (inpatient stay is excluded) will be applied to determine to which visit an ET valid on-treatment assessment can be mapped to. Visit windows are defined in Table 8 below.

If a subject didn't complete the Part A, his/her ET assessment will not be mapped to Part B visits, i.e. Visit 14 to 23.

Table 8: Visit Window Definition

Analysis Visit to be Mapped to	Target Study Day	Visit Window
Visit 6	15	[9, 18]
Visit 7	22	[19, 25]
Visit 8	29	[26, 32]
Visit 9	36	[33, 43]
Visit 10	50	[44, 57]
Visit 11	64	[58, 71]
Visit 12	78	[72, 85]
Visit 13	92	[86, 98]
Visit 16	99	[99, 102]
Visit 17	106	[103, 109]
Visit 18	113	[110, 116]
Visit 19	120	[117, 127]
Visit 20	134	[128, 141]
Visit 21	148	[142, 155]
Visit 22	162	[156, 169]
Visit 23	176	[170, 183]

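### Required contraception stops at study end, 29 days after a completer's last samidorphan dose, while exclusion 10 bars planned pregnancy for 60 days after dosing: a minor misalignment to correct for women

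*Protocol*

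**What the plan says.** Two places set the contraception duty, and both tie it to the study rather than to dosing. Inclusion 10 (Protocol 7.1) reads "Subject agrees to use an acceptable method of contraception for the duration of the study", and Section 8.4.2 reads "All subjects must agree to use an acceptable method of contraception for the duration of the study". The accepted combination is a condom plus an intrauterine device or a hormonal method. Surgically sterile subjects and postmenopausal women are exempt. Neither place gives a period after the last dose, and no other section of the protocol or SAP adds one.

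Exclusion 10 (Protocol 7.2) does use a period after dosing. It excludes a woman who is pregnant, breastfeeding or "planning to become pregnant within 60 days of the last study drug administration".

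Section 8.1.2 places the last samidorphan dose on the evening before Visit 23 (Day 176), and Section 9.1 confirms "No samidorphan dose will be administered onsite during Visit 23/ET". Follow-up ends at Visit 25, Day 204, and Table 2 keeps olanzapine going until then. Section 9.1 also says "Study drugs include samidorphan and matching placebo tablets, and olanzapine tablets, all for oral administration", so olanzapine counts as a study drug. After early termination (ET), Section 7.3 says only that "subjects should be encouraged to return for follow-up visits 2 and 4 weeks after the ET visit".

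**The concern.** The protocol treats the 60 days after dosing as a time when a participant should not be planning a pregnancy, but it releases her from contraception about halfway through that time if it is counted from samidorphan. A woman with no plan to conceive passes exclusion 10 and may stop contraception at Visit 25 within the rules. An entry screen on intent does not prevent an unplanned conception or a change of mind.

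At stake is participant safety after exposure to a new chemical entity. Section 5.4 cites repeated dosing of 1 to 10 mg for up to 12 weeks. This trial gives up to 20 mg for up to 24 weeks. After the final follow-up visit, Section 13.5 collects events only if the investigator thinks they may be related to study drug.

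Two further looseness points belong here. Exclusion 10 does not say which drug starts its 60 days. And because the duty follows the study and not the dose, cover after early termination depends on follow-up visits that are encouraged but not required.

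**Working it through.** This is calendar arithmetic on nominal study days.

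**Inputs**
- Visit 23: Day 176, ±2 days (Table 2).
- Visit 25: Day 204, ±2 days (Table 2).
- Last samidorphan dose: the evening before Visit 23 (Section 8.1.2). Subjects randomized to placebo in Part A switch to samidorphan in Part B, so this applies to completers in all four arms.
- Last in-study olanzapine dose: Visit 25 (Table 2, footnote 10).
- Planned-pregnancy period: 60 days (exclusion 10).

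**The plan's own figure.** Visit 25 is four weeks after Visit 23: 176 + 28 = 204, as the schedule states.

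**Completers, counted from samidorphan**
- Last dose: 176 − 1 = Day 175.
- Covered: 204 − 175 = 29 days, and 29/60 = 48%.
- Not covered: 60 − 29 = 31 days.
- Shortest cover with windows: (204 − 2) − (175 + 2) = 25 days, leaving 35.
- Longest cover with windows: (204 + 2) − (175 − 2) = 33 days, leaving 27.

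**Completers, counted from olanzapine** (the literal reading of study drug)
- The 60 days start on Day 204 and end on 204 + 60 = Day 264.
- The duty ends on Day 204, so all 60 days fall after it.

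**Where each reading of exclusion 10 ends**
- Samidorphan start: 175 + 60 = Day 235.
- Olanzapine start: Day 264.
- Difference: 264 − 235 = 29 days.

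**Early terminators.** Let k be the days from last samidorphan/placebo dose to the ET visit. If both follow-up visits are attended, cover is 28 + k days and the shortfall is 32 − k. With k = 1 that is 29 and 31, the same as for a completer. If a woman declines follow-up and her study is taken to end at ET (an assumption, since the protocol does not say), the shortfall is 60 − k. The documents put no upper limit on k, so no range is given.

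**The case against.** The strongest reply is that the two rules do different jobs. Exclusion 10 screens intention at entry, and Section 8.4.2 governs conduct during the study. Nothing obliges them to have the same length, and together they leave only unplanned conception, or changed plans, after the last visit. That stands, and it is why the rules are called misaligned and not contradictory. What the documents lack is any reason for guarding 60 days against planned conception and a shorter time against unplanned conception.

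A second reply is that no harm is shown. That also stands. A reader might infer that 29 days is unsafe or that 60 days is required. Neither follows. The only statement on persistence, in Section 8.4.4, concerns altered opioid response over several days, which does not settle reproductive risk either way. The Investigator's Brochure and the site consent forms are not part of these two documents and may say more.

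Third, a reader might want to tidy exclusion 10 by starting its 60 days at the last samidorphan or placebo dose. On the literal reading that shortens an existing safeguard by 29 days, from Day 264 to Day 235. The same starting point would also be undefined for women who leave during the olanzapine lead-in. The protocol expects 20% of 350 enrolled subjects, or 70 of both sexes, to leave before randomization.

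Finally, a reader might take the SAP's rule in Section 3.11.1.3, "If an ET visit is within 7 days after the last dose of samidorphan/placebo", as a limit on the time since last dose. It only decides whether an ET assessment counts as on treatment, so it cannot be used to size the gap for early terminators.

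**Conclusion.** The misalignment holds as a minor participant-safety point. For a completer, 31 of the protocol's own 60 days carry no contraception duty if counted from samidorphan (27 to 35 with visit windows), and all 60 if counted from the last in-study olanzapine dose. The 31-day figure assumes attendance on schedule and a last dose on the evening before Visit 23. The 60-day figure assumes that study drug in exclusion 10 includes olanzapine, as Section 9.1 defines it.

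The conclusion takes 60 days as the sponsor's own period and makes no claim that it is the right length. No endpoint, power or error rate depends on it.

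**What to change.** Amend Section 8.4.2 and inclusion 10 so that women who are not exempt use contraception *until the end of study participation and, if any samidorphan or placebo was taken, until 60 days after the last such dose, whichever is later*. That is Day 235 for a completer. Women who leave during the olanzapine lead-in keep the present rule. The duty for men stays as it is, since exclusion 10 concerns pregnancy in the participant.

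Do not shorten exclusion 10. Either leave its wording alone, or have the sponsor state which drug starts the 60 days and acknowledge that a samidorphan/placebo start moves its literal end from Day 264 to Day 235. If the Investigator's Brochure supports another length, use that length in all three places.

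The cost is protocol and consent wording, with no added visit or test. Completers carry about 31 more days (235 − 204) of a duty that cannot be checked at a visit. Early terminators who attend follow-up carry 31 more days if the last dose was the evening before ET, and fewer if dosing stopped earlier. Those who decline follow-up carry more, because their study participation ends sooner.
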